8.1 Inclusion Criteria

- People diagnosed with PD.
- Age 18 or older
- Able to provide consent to take part

8.2 Exclusion Criteria

Have already taken part, or are an active member in a SParky Samba group

9 Recruitment, Screening & Registration

9.1 Participant Identification

Participants will be identified in a range of secondary care provisions and movement clinics that cater for people diagnosed with PD, which include neurology and care of the elderly. Clinical staff (consultants, nurses and PD specialist nurses) will identify potential participants for recruitment alongside social media and advertising through local PD focussed organisations such as Parkinson's UK Cymru. Participants may also self-refer by contacting the trial team on the advertised e-mail address.

9.2 Screening Logs

A screening log of all ineligible and eligible but not consented and/or not approached individuals will be kept at each site so that any biases from differential recruitment can be detected. When at site, logs may contain identifiable information but this **must** be redacted prior to being sent to the CTR. The screening log should be sent to the SParky Samba Trial email every month (see section 16 for further detail on data monitoring/quality assurance).

9.3 Recruitment Rates

A total of 60 participants will be recruited at an expected rate of 6 per month (2 participants per site per month).

9.4 Informed Consent

The participant's informed consent must be obtained using the electronic trial Consent Form (eCF), which follows the PIS. The participant should be given sufficient time after the initial invitation to participate before being asked to sign the eCF. Informed consent must be obtained prior to the participant undergoing trial activities. Consent may be facilitated by trial trained healthcare research delivery workforce staff at the SParky Samba activated sites.

The REDCap e-consent module will be used for e-consent in Sparky Samba. A pdf copy of the consent form will be sent to the participant by email for their records.

Please note, only when informed consent has been obtained from the participant via REDCap and they have been registered into the trial can they be considered a trial participant.

The right of the participant to refuse to participate in the trial without giving reason must be respected. Similarly, the participant must remain free to withdraw at any time from the protocol intervention without giving reasons and without prejudicing his/her further treatment.

9.5 Registration & Randomisation

9.5.1 Registration

Participants will be added to the REDCap database to be able to complete their consent and their baseline assessments. When they have completed these assessments, they will then be randomised. Participants must be randomised within 2 weeks of their registration.

9.5.2 Randomisation

Participants will be randomised to the intervention or activity as usual in a 1:1 ratio, stratified by disease burden (Hoen and Yahr stage). The randomisation system will be designed, tested and

implemented via a REDCap database hosted by the CTR. Dummy randomisations will be completed via the database to ensure that the groups balance ahead of live randomisations. Full details of the randomisation procedure will be specified in a separate randomisation plan.

10 Withdrawal & Lost to Follow-up

10.1 Withdrawal

Participants have the right to withdraw consent for participation in any aspect of the trial at any time. The participants care will not be affected at any time by declining to participate or withdrawing from the trial.

If a participant initially consents but subsequently withdraws from the trial, clear distinction must be made as to what aspect of the trial the participant is withdrawing from including:

- Withdrawal from intervention
- Partial withdrawal from further data collection (e.g. questionnaires, clinical assessments, process evaluation)
- Complete withdrawal from further data collection

Participants will not be able to request deletion of any of the data that they have provided which links with any of the trial outcomes. However, if they have provided any personally identifiable data (e.g. name, email address) then as part of the withdrawal process, they can request that the CTR delete this type of information that they hold from their databases.

The withdrawal of participant consent shall not affect the trial activities already carried out and the use of data collected prior to participant withdrawal. The use of the data collected prior to withdrawal of consent is based on informed consent before its withdrawal.

In all instances participants who consent and subsequently withdraw should complete a withdrawal form (see Withdrawal Form in trial pack) or the withdrawal form should be completed on the participant's behalf by the researcher/PI based on information provided by the participant. This withdrawal form should be sent to the SParky Samba Trial email and any queries relating to potential withdrawal of a participant should be forwarded to the SParky Samba Trial email.

10.2 Lost to follow up

Participants who are absent for more than 3 consecutive weeks from intervention sessions will be contacted by the research team to provide assistance or determine of a participant wants to withdraw. If participants are uncontactable after three attempts (three each phone call and/or email) and they continue to be absent from the intervention sessions no further action will be taken. They will not be regarded as lot to follow up until they fail to complete the 12 week follow up assessment (see below).

Participants not completing follow-up assessments on-line, or who do not attend clinic for follow-up assessments will be contacted by the research team in an attempt to ensure follow-up is completed, this may include providing telephone support to complete patient reported outcomes. If the person does not respond after three contact attempts (three each phone call and/or email), then they will be regarded as lost to follow-up.

11 Trial Intervention

11.1 SParky Samba Intervention

SParky Samba is a samba-based rhythm/ drumming intervention delivered within the community for people with PD. The setting is determined by local availability of facilities, which are chosen by SParky Samba leaders based on their geographic location and accessibility for group members.

The group is facilitated by either a local Samba musician, or a regular member of the group who has been trained by the musician to deliver SParky Samba sessions. The group size is usually around 8-15 participants but there is no minimum or maximum number of participants required for any given session.

In their first session participants will be offered a choice of instrument that is suitable for their range of motion. This could range across tamborims, Snare drums (Caixa), Agogo bells, Surdos, Ganzás / Chocalho (shakers), Cuíca, Timbal, Pandeiro, and the Repinique.

During each session, participants will be instructed to follow a sequence of rhythms, as guided by the facilitator. Each rhythm is broken down into smaller sections with sub-groups (grouped by instrument) concentrating on their own section before coming together. The band leader often carries a Repinique, as well as using Apitos (whistle) to signal breaks to participants.

Each session will last approximately 60 minutes with time either side for the set-up and break down of instruments and seating.

Participants will be asked to attend as many sessions as possible, ideally weekly over a period of 12 weeks following randomisation. Participants will be encouraged to attend at least 6 consecutive sessions and a minimum of 8 in total (completion of 8 sessions in total will be regarded as adherent to the intervention). The costs of participant travel to attend Sparky Samba sessions will be reimbursed. Alternatively, travel arrangements will be made upfront on behalf of the participant if they prefer.

The PPI Group have been involved in the co-production of patient facing materials and the intervention definition through a series of stakeholder workshops that have informed phase 2 of the trial. The trial team will continue to work with the PPI Group throughout the trial in co-production of documents for publication and an Intervention Manual.

11.2 Intervention Comparator

Participants randomised to the activity as usual control group will be asked to continue with their normal activities and attend any social or support groups they would normally attend over the 12 weeks. Following completion of the 12-week follow-up assessment they will be offered the opportunity to join their local SParky Samba group.

11.3 Adherence

Participants will be emailed a link to the REDCap database each week following the session to complete a self-report attendance checklist.

Group facilitators will also be asked to complete a checklist following each session during the recruitment and intervention delivery period.

12 Trial Procedures

Recruitment and follow-up:

Participants will be identified at clinical sites or via social networks/ word of mouth and eligible participants will be approached and provided with trial information prior to giving informed consent. Participants will be assessed at baseline and at 12 weeks post randomisation following intervention delivery. The intervention delivery period will commence at randomisation (to occur within 2 weeks of baseline assessment) and will last for a period of 12 weeks. With the addition of the process evaluation (see below), participants are expected to be in the trial for no longer than 16 weeks.

Data collection/assessments and blinding

Outcome data will be collected through a combination of patient reported measures completed directly within the database and in person assessments conducted by research staff at site. If a participant choses, they will be able to complete the patient reported outcomes on paper copies if they prefer (see data management section 16.2). participants may be supported with on-line or paper completion at the hospital research visit by the trial research staff, or at home by one of the core trial team members via telephone. Due to the nature of the intervention and the pragmatic design of the trial, researchers collecting assessment data will not be blind to the allocation of participants. In an effort to reduce bias of rating the UPDRS, this assessment will be videoed by the assessor at site and rated independently by an expert blinded to allocation. The measures included in SParky Samba do not form part of routine care, although PD specific measures such as UPDRS and Hoen and Yahr may be used by clinicians ad-hoc as part of their routine assessment of participants at clinic appointments.

Intervention (and intervention comparator) adherence data will be provided through participant self-report and self-report from SParky Samba group facilitators.

Process Evaluation:

The process evaluation will utilise qualitative data (semi-structured interviews with intervention staff) and quantitative data (structured reflections by members of the research team delivering the intervention and a purpose developed fidelity questionnaire as well as data on completed visits) to assess fidelity (whether the intervention has been delivered as intended and as a measure of quality assurance), and the key mechanisms of change. Participants and their support partners will be asked to complete a structured questionnaire that focusses on their views of the trial and of the intervention. We will also attempt to contact any participants who drop out of the intervention to ascertain reasons for discontinuing. A more detailed protocol for the process evaluation will be maintained separately in Document 'SParky Samba Feasibility RCT Process Evaluation'.

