12.1 Assessments

Table 2. SParky Samba Outcome Assessments

Construct	Measure	Time to complete	Time points
Motor	UPDRS III: We will use section III of the Unified Parkinsons Disease Rating Scale to assess global motor function in participants	15 min	Baseline and 12 weeks
	Freezing of Gait questionnaire (FOG) : this is a patient self report measure designed to assess the severity of gait freeing in people with PD.	5 min	Baseline and 12 weeks
	Dresden Falls Questionnaire — this is a patient report questionnaire designed to assess the risk and severity of falls, a common symptom in people with PD.	5 min	Baseline and 12 weeks
	MiniBEST Test in this assessment participants are assessed across dynamic balance, functional ability and gait.	15 minutes	Baseline and 12 weeks
	Physical Activity in the Elderly (PASE) questionnaire this questionnaire is designed to capture the level of physical activity across a range of usual activities over the past 7 days.	5 min	Baseline and 12 weeks
Cognitive	Montreal Cognitive Assessment (MoCA) – we will use the truncated on- line version of the MoCA, known as Expresso, to assess cognitive function in participants. This is well validated for assessing cognitive function in pe	6 minutes	Baseline and 12 weeks
Quality of Life	Parkinson's Disease Quality of Life Questionnaire [8 items] – PDQ-8; This is a self-completion participant reported outcome designed to address aspects of functioning and well-being for those affected by Parkinson's disease. The PDQ-8 asks one question from each of the domains of the longer PDQ-39; activities of daily living, attention and working memory, communication, depression, quality of life and social relationships.	5 minutes	Baseline and 12 weeks
Self Efficacy	Oxford Participant and Activities Questionnaire (OxPaq)— this is a validated self-report questionnaire designed to assess the degree of activity and participation of those with chronic conditions taking part in community based interventions	5 minutes	Baseline and 12 weeks
	The Lorig Self Efficacy (scale will be utilised to measure self-efficacy related to exercise (exercise sub-scale only)	5 minutes	Baseline and 12 weeks

Figure 3. Schedule of enrolment, interventions and assessments

Procedures	Visits (insert visit numbers as appropriate)

	Baseline V	isit (week 0)	Intervention	Follow Up Visit (week 12 ± 5 days)			
	At home (Day -3;	At hospital (Day 0)	Delivery (Day 0 – Day 84)	At home (Day 85	At hospital Day 88 ±2		

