15.1 Main Analysis

Key demographic data will be summarised using descriptive statistics. For feasibility outcomes, recruitment will be assessed as the percentage of eligible people who provide consent to participate in the trial; retention as the percentage of participants recruited who complete the 12-week follow-up assessment; adherence as the percentage of recommended intervention or social control sessions completed. Feasibility criteria will be assessed according to a traffic light system with green (proceed to full effectiveness RCT) if all criteria listed in section 5.3 are in the green zone; amber (requiring adjustment before proceeding to full RCT) if all criteria are either in the amber or green zone; and red (do not progress to full RCT unless major changes are implemented) if at least one criterion is in the red zone. For secondary outcome measures we will calculate descriptive summaries such as mean and standard deviation, and 95% confidence intervals of participants' percentage changes from baseline to 12-week follow-up. This will provide estimates of effect size and variability of drumming-induced changes for use in power calculations for a future RCT.

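### Comparator adherence is promised and analysed but never defined, and no described instrument systematically records whether controls attended SParky Samba or took up drumming or dance during the 12 weeks

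*Protocol*

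**What the plan says.** Section 12 (data collection, assessments and blinding) commits to adherence data in both arms: "Intervention (and intervention comparator) adherence data will be provided through participant self-report and self-report from SParky Samba group facilitators".

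Section 11.3 describes two instruments. For participants: "Participants will be emailed a link to the REDCap database each week following the session to complete a self-report attendance checklist". For facilitators: "Group facilitators will also be asked to complete a checklist following each session during the recruitment and intervention delivery period".

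Section 11.1 defines adherence for the samba arm: "completion of 8 sessions in total will be regarded as adherent to the intervention". There is no counterpart for controls, who under Section 11.2 "will be asked to continue with their normal activities and attend any social or support groups they would normally attend over the 12 weeks" and are offered a place in their local samba group once the 12-week assessment is done.

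Section 15.1 nevertheless analyses "adherence as the percentage of recommended intervention or social control sessions completed". Section 5.2 calls the comparator an active social control, whereas the Synopsis and Sections 4.1, 6 and 11.2 describe activity as usual.

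The schedule in Section 12.1 (Figure 3) has one adherence row, labelled for the intervention. Read by column order, it is marked during delivery and again at the Day 85 home follow-up.

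**The concern.** The protocol commits to a comparator quantity, and to analysing it, without saying what it is or how it is obtained. A checklist triggered by a session has no obvious trigger for someone who has no sessions, and samba facilitators cannot report on groups they do not run.

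Section 4.1 says the comparison should help separate the benefits of ordinary social activity from those specific to samba, which requires knowing what controls did. Section 4 itself names drumming, dance and music-based movement as activities with apparent benefit in Parkinson's disease. The only exclusion in Section 8.2 is past or current SParky Samba membership, and Section 7 places sites near existing groups. Section 15.1 intends the results to inform power calculations for a later trial. If some controls attend samba early, or start something similar because of the trial, the difference between arms shrinks. Whether a control arm stays free of such exposure is also a feasibility question for that later trial. Exposure that was not recorded cannot be recovered by analysis.

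**Working it through.** **Step 1: which described sources could show control exposure?**

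- *Participant checklist (11.3).* Weekly, sent after the session. The arm is not stated and the content is not given. It might go to controls; the text does not say so.
- *Facilitator checklist (11.3).* Completed after each samba session. If it lists attendees, it could show a control at SParky Samba. It cannot show drumming or dance elsewhere.
- *Day 85 adherence entry (Figure 3).* Not tied to a session, but labelled as intervention adherence, with no description of its content.
- *PASE (12.1).* "this questionnaire is designed to capture the level of physical activity across a range of usual activities over the past 7 days". At week 12 it covers one week of the twelve, and it is not described as identifying samba, drumming or dance.
- *OxPAQ (12.1).* "designed to assess the degree of activity and participation of those with chronic conditions taking part in community based interventions". It measures degree of participation and is not an activity log.
- *Process evaluation questionnaire (12).* Described as covering views of the trial and the intervention. Details are in a separate document that is not shown.

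No source is described as recording control activity over the 12 weeks. One might show part of the samba attendance.

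**Step 2: is there a denominator for the control part of Section 15.1?** It would need a number of recommended control sessions. Section 11.2 recommends none, so the percentage is undefined for controls.

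**Step 3: how precise would a control exposure rate be?** Section 14.3 states a half-width of at most 13 percentage points. With n = 60 and p = 0.5:

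1.96 × √(0.25/60) = 0.1265, or 12.65 points (Wilson 12.26, Clopper-Pearson 13.19).

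The stated figure reproduces by Wald or Wilson. A control exposure rate rests on 30 people (Synopsis):

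1.96 × √(0.25/30) = 0.1789, or 17.9 points (Wilson 16.8, Clopper-Pearson 18.7).

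Other Clopper-Pearson results for n = 30:

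- 0 of 30 exposed: one-sided 95% upper limit 1 − 0.05^(1/30) = 9.5%
- 3 of 30 exposed: 95% interval 2.1% to 26.5%
- 6 of 30 exposed: 95% interval 7.7% to 38.6%

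**Step 4: illustration of dilution.** The documents give no exposure rate. Assume that a share c of controls is exposed and obtains the full effect. The observed difference is then (1 − c) times the true one, and the sample size a later trial needs rises by 1/(1 − c)²:

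- c = 5%: 1/0.9025 = 1.11
- c = 10%: 1/0.81 = 1.23
- c = 20%: 1/0.64 = 1.56
- c = 30%: 1/0.49 = 2.04

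Both the rates and the full effect are assumptions.

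**The case against.** A reader might infer that control exposure cannot be measured at all and that the trial must end without a contamination rate. The documents do not support that. Section 11.3 does not restrict its participant checklist to one arm, the forms are not shown, the schedule has an adherence entry at Day 85, facilitator checklists might reveal a control at a session, and the process evaluation has its own protocol. These points limit the claim to what is described. They do not supply a definition of comparator adherence or a stated means of collecting it.

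A reader might also take the absence of a limit on group size in Section 11.1 to mean that controls can walk in. That sentence concerns how many people a session needs, not who may attend. Controls are offered samba only after the 12-week assessment, and existing members are excluded. These are real safeguards, although no check on early attendance is described.

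The strongest objection is that dance, music or exercise groups that controls already attend are part of an activity-as-usual comparator. A later trial with the same comparator would have the same background, so sizing on a difference that includes it is appropriate. This stands. Only early SParky Samba attendance, or newly started rhythm-based activity, counts as exposure of concern.

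It is also fair that the dilution factors would apply to any trial and that a full effect from other groups is implausible. Thirty controls could not reliably separate 5%, 10% and 20%. Weekly questions about drumming might themselves prompt uptake, which argues for asking once, at the end.

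**Conclusion.** The point holds as a gap between what Sections 12 and 15.1 commit to and what Sections 11.1 to 11.3 provide. Comparator adherence is undefined, the control sessions that Section 15.1 counts do not exist, and no described instrument systematically captures early samba attendance or newly started drumming or dance among controls. Some samba attendance might still show in facilitator records.

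The effect on the results cannot be sized from the documents. The factors of 1.11 to 2.04 are illustrations for assumed exposure of 5% to 30% with full effect in those exposed; they are not evidence that dilution will occur. The conclusion assumes that the unseen forms contain no more than the protocol describes. If the weekly checklist or the Day 85 form already asks controls about these activities, only the wording needs reconciling. This is a cheap and worthwhile improvement, not a flaw that undermines the trial.

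**What to change.** 1. On the adherence form already scheduled for the Day 85 home follow-up, ask both arms whether and how often they attended SParky Samba, or any other drumming, dance or music group, during the 12 weeks, and whether each activity was usual or newly started.
2. Add a field to the facilitator checklist for attendance by any control participant before the 12-week assessment.
3. In Section 15.1, report the control exposure rate with its confidence interval, keeping usual activity (part of the comparator) apart from new samba or drumming exposure.
4. Reconcile the active social control in Section 5.2 and the control sessions in Section 15.1 with the activity-as-usual comparator in Section 11.2, and state in Section 12 what comparator adherence means or remove the term.

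The cost is a few extra questions, one checklist field and some protocol wording. The answers rely on 12-week recall, and the rate from about 30 controls will be imprecise (worst-case 95% half-width about 18 points). Asking once at the end avoids prompting controls every week.
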